Study Title: Engaging Patients in Colon Cancer Screening Decisions During COVID-19

Document Title: Design and Analysis plan for the randomized controlled trial in the PRIMED COVID Supplement Study

PIs: [name] ([contact]) and [name] ([contact])

Statisticians: [name] and [name]

Clinical Trials.gov: NCT04548531

Date: August 25, 2021

Background: Thousands of colonoscopies were cancelled during the initial surge of the COVID-19 pandemic. As facilities resumed elective health care services, many faced additional challenges such as longer wait times due to backlogs, limits on volume due to new requirements for infection control, and some patients were hesitant to reschedule. Informing patients about their CRC screening options, including home-based stool tests and colonoscopy, and eliciting and addressing their concerns about testing may improve decisions and help increase overall screening rates. However, studies suggest clinicians tend to recommend one screening test with little discussion of other options, falling short of the shared decision making (SDM) ideal. Whether a SDM approach would work with patients who may be hesitant to seek care during the pandemic is not clear. The purpose of this study was to determine whether a decision aid plus telephone coaching would increase colorectal cancer (CRC) screening and improve patient reports of shared decision making (SDM).

Design: Randomized controlled trial where patient participants were randomized 1:1 into either intervention or control arms.

On June 2, 2020, the co-investigators from the Massachusetts General Hospital Gastroenterology Department extracted a list of patients aged 45-75, with preferred language of English or Spanish, who had a screening or surveillance colonoscopy that was cancelled, who had a referral for a screening colonoscopy that had not been processed, or who should have been contacted by the GI department to schedule a screening colonoscopy but had not been due to COVID-19 restrictions since March 15, 2020.

The intervention mailings went out in four waves, about two weeks apart, between September 10, 2020 and October 22, 2020. Participants in the intervention arm received a decision worksheet in the mail followed by a call from a decision coach. A subset of participants across both arms were selected to receive a survey. Staff mailed a survey to the selected subset of control and intervention participants about 8 weeks after the intervention packet was mailed to their wave. The survey packet included a cover letter, an information sheet, an incentive (\$10 gift card), the survey and a return envelope. Patients were able to complete the survey by mail, online via REDCap, or over the phone with study staff. Staff made up to three reminder phone calls and sent a reminder mailing to non-responders with 3 additional reminder calls. Spanish-speaking research staff conducted reminder calls for Spanish-speaking participants. Staff conducted chart review to collect screening tests completed within 6 months.

Randomization and blinding: The study statistician used a computer random number generator to randomly select 800 eligible patients, assign each to intervention or control arm, and to one of 4 waves. All 800 patients were followed to track colon cancer screening tests completed and a subset in each wave were randomly selected to receive a survey to measure patient-reported outcomes. The staff who entered the data from the paper surveys and who conducted chart review to collect screening were blinded to the assignment. The statistician analyzing the results was not blinded to the assignment.

Outcomes:

Screening uptake: study staff examined medical records to determine receipt of any colorectal cancer screening test for all subjects within 6 months.

The following measures were collected in the patient survey:

SDM Process Scale: 4-item survey asks about discussion of stool test, pros and cons of colonoscopy and patient's screening preference. Total scores range from 0-4 with higher scores indicating higher shared decision making. Patients who indicated that they did not talk with anyone about CRC screening received a SDM Process score of 0.

SURE scale: the brief 4-item version of the decisional conflict scale. A point is given for each "yes" response for total scores 0-4 and we report the percentage receiving the top score of 4, which indicates no decisional conflict.

Screening preference: One item asked patient's preferred approach to screening (with responses: colonoscopy, stool-based test, delay screening, not sure).

Additional measures were collected to describe the sample and used as covariates including whether or not the patient had a CRC discussion with health care provider in the past two months, PROMIS Scale v1.2-Global Health Physical 2a, Single Item Literacy Screener, CRC screening and history, COVID-19 worry, decision worksheet use and decision coaching exposure. Basic demographics for the full sample were collected via chart review.

Sample Size: The sample size of 800 was determined based on the screening uptake, with 800 participants, the study had 81% power to detect a difference of 10% in rates. For the survey, we assumed a 60% response rate and as a result, planned to invite about 500 patients (250 in each arm) to obtain 300 responses. With 300 survey responses, the study had 80% power to detect a difference of 0.32 standard deviation (SD) for the SDM Process score. Studies have found effect sizes ranging from 0.39SD – 0.88SD for SDM Process when comparing sites that used formal

decision support (coaching or decision aids) and those that did not. For dichotomized survey outcomes (% SURE top score and % prefer screening), with 300 responses, we had 80% power to detect a 13% difference, from 70% to 83%.

Statistical methods: Sample demographics and characteristics were compiled and compared to evaluate the balance between the two arms. Responders and non-responders to the survey were compared between arms to evaluate potential non-response bias.

The following hypotheses were evaluated using an intention to treat approach, and patients were analyzed based on their assigned arm.

1. Compared to the control group, patients in the intervention arm will be more likely to have a screening test within 6 months (the percentage of patients who had either stool test or colonoscopy in each arm compared using a Fisher Exact test). We also used cumulative incidence function to compare time to screening completion.
2. Compared to the control group, patients in intervention arm will report higher SDM scores (compared mean scores using a two sample t-test).
3. Compared to the control group, patients in the intervention arm will (3a) be more likely to have a clear preference for colon cancer screening (either colonoscopy or stool-based test) and (3b) have less decisional conflict (i.e. higher percentage of SURE top scores). We compared the percentage of patients with these outcomes between arms using Chi-square analyses.

In a pre-specified analysis, we explored the heterogeneity of treatment effects (HTE) to identify differential treatment effects among subgroups of patients stratified by sex as a biological

variable, age, race/ethnicity, education, overall health, prior screening history, COVID worry and interaction with decision coach. We used linear or logistic regression models to test the interaction between study arms and these factors. We highlighted the subgroups that presented differential effects regardless the significance of p values for the intervention and subgroup interaction. These results are exploratory in nature as the study was not powered for any of the subgroup analyses, and there was no attempt to control for potential biases.

CONSORT:

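### With 300 responses, the planned chi-square test has about 76% power for 70% versus 83% on the dichotomised survey outcomes, not the stated 80%

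*SAP*

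**What the plan says.** The SAP, under Sample Size, bases the total of 800 on screening uptake and then treats the survey separately. It assumes a 60% response rate and says the team "planned to invite about 500 patients (250 in each arm) to obtain 300 responses". Two power statements follow for that number of responses. One is for the SDM Process score: "With 300 survey responses, the study had 80% power to detect a difference of 0.32 standard deviation (SD) for the SDM Process score". The other covers the two binary survey outcomes, top SURE score and preference for screening: "with 300 responses, we had 80% power to detect a 13% difference, from 70% to 83" per cent.

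Under Design, the SAP says that "patient participants were randomized 1:1 into either intervention or control arms". Under Statistical methods, hypothesis 3, it names the analysis for the binary outcomes: "We compared the percentage of patients with these outcomes between arms using Chi-square analyses". Neither the SAP nor the protocol gives a significance level or says whether tests are one-sided or two-sided.

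**The concern.** The sentence gives everything needed to check it except alpha: the number of responses, both rates and the claimed power. At the conventional two-sided 0.05, these inputs do not give 80%.

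It is the only planning figure for hypotheses 3a (clear preference for screening) and 3b (less decisional conflict). If power is overstated, the risk of missing the stated difference is understated. A reader who uses the SAP to judge a null result on either outcome would then think the study somewhat better able to detect that difference than it was.

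**Working it through.** **Inputs (SAP)**

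- Responses: 500 invited × 0.60 = 300. The response rate is already used up in the 300, so no further inflation is hidden.
- Per arm: 250 invited × 0.60 = 150.
- Rates: p1 = 0.70, p2 = 0.83, difference 0.13.
- Test: chi-square, with no continuity correction mentioned.
- Alpha: not stated. Two-sided 0.05 is assumed, so z = 1.960.

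**Does the assumed alpha fit the SAP's other figures?**

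- SDM Process score, 0.32 SD, 150 per arm: Φ(0.32 × √(150/2) − 1.960) = Φ(2.771 − 1.960) = 79.1%. The t-test gives 78.9%. Solving for 80% gives (1.960 + 0.842) × √(2/150) = 0.3235 SD, which prints as 0.32. One-sided 0.05 would give 87.0%.
- Screening uptake, 10 points, 400 per arm: 81.3% from a base rate of 40% and 80.9% from 45%, against the stated 81%. The base rate is not stated, so these are assumptions. One-sided 0.05 would give about 88%.

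At two-sided 0.05 the SDM figure reproduces within rounding, and the uptake figure reproduces at those base rates.

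**The disputed figure, 150 per arm, two-sided 0.05**

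Pooled formula, the usual approximation to the Pearson chi-square test:

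- Mean rate = (0.70 + 0.83)/2 = 0.765
- SE under the null = √(2 × 0.765 × 0.235/150) = 0.04896
- SE under the alternative = √((0.70 × 0.30 + 0.83 × 0.17)/150) = √(0.3511/150) = 0.04838
- Power = Φ((0.13 − 1.960 × 0.04896)/0.04838) = Φ(0.704) = **75.9%**

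Other routes:

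| Method | Power |
|---|---|
| Unpooled: Φ(0.13/0.04838 − 1.960) = Φ(0.727) | 76.6% |
| Arcsine: h = 0.3093; Φ(0.3093 × √75 − 1.960) = Φ(0.719) | 76.4% |
| Exact enumeration, Pearson chi-square | 76.4% |
| Exact enumeration, Yates-corrected chi-square | 72.0% |
| Exact enumeration, Fisher | 72.2% |
| One-sided 0.05, uncorrected | 84.7% |
| One-sided 0.05, continuity-corrected | 81.2% |

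No two-sided method reaches 80%. Mildly unequal response between arms (ratios 0.8 to 1.25) gives 75.0% to 76.0%.

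**What 80% power would require**

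- At 70% versus 83%, unpooled: n = (1.960 + 0.842)² × 0.3511/0.13² = 163.1, so 164 per arm (328 in total).
- At 70% versus 83%, pooled: 165.8, so 166 per arm (332 in total).
- At 150 per arm, the rate detectable from 70% is 83.49% (unpooled), 83.53% (arcsine) or 83.60% (pooled). The difference is 13.5 to 13.6 points.

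**Where 13 probably came from.** The unpooled detectable difference is 13.49 points, which rounds down to 13. The pooled and arcsine values would round to 14.

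**The case against.** The best defence is that the sentence reports a rounded detectable difference and is not a miscalculation. Power was fixed at 80%, and 13.49 points was printed as 13, much as 0.3235 SD was printed as 0.32. This is the likely origin. It works only for the unpooled formula, however, and it does not make the sentence true: explicit rates are given, and at those rates power is 76%. The same kind of rounding costs about 1 point of power in the SDM sentence and about 4 points here.

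Second, alpha is unstated and the hypotheses are worded directionally. A one-sided 0.05 test with continuity correction gives 81.2%, close to the stated figure. But one-sided 0.05 does not fit the SDM figure (87.0% against 80%), and an ordinary chi-square test is two-sided. What stands is that two-sided 0.05 is an assumption and should be labelled as one.

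Third, the consequences are modest, and this stands. The 800 was set on screening uptake, the SAP is dated August 2021 and written in the past tense, and no test or population would change. The 70% base rate is also given without a source, and power is sensitive to it: by the pooled formula, 13 points from 72% gives 78.5% and from 75% gives 83.0%. A null result will also be judged mainly on its confidence interval. These points limit the importance of the error but do not correct the figure.

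**Conclusion.** The stated 80% is not what the planned test delivers at the stated rates. With 150 responses per arm, power for 70% versus 83% is about 76%, a shortfall of 3.4 to 4.1 points across the uncorrected methods. The type II error is about 24% instead of 20%. Put differently, the plan is about 28 to 32 responses short of its claim, or the detectable difference is understated by about half a percentage point.

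This rests on two-sided alpha 0.05, an uncorrected chi-square test and an even split of the 300 responses. A continuity correction would lower power to about 72%, but the SAP does not call for one. Only the planning statement for hypotheses 3a and 3b is affected.

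**What to change.** Replace the sentence in the SAP's Sample Size paragraph with one of these:

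- 300 responses (150 per arm) give 76% power to detect 70% versus 83%, using a Pearson chi-square test without continuity correction at two-sided alpha 0.05; or
- 300 responses (150 per arm) give 80% power, for the same test and alpha, to detect 70% versus about 83.6%.

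The authors should confirm that two-sided 0.05 and the uncorrected test are what they used; if not, they should state what was used and recompute. The cost is one sentence and a slightly less favourable figure. Enrolment, data and analysis do not change.

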PARTNERS HUMAN RESEARCH COMMITTEE PROTOCOL SUMMARY

Answer all questions accurately and completely in order to provide the PHRC with the relevant information to assess the risk-benefit ratio for the study. Do not leave sections blank.

PRINCIPAL/OVERALL INVESTIGATOR

[name]

PROTOCOL TITLE

Promoting informed decisions about rescheduling colonoscopies delayed due to COVID-19 (PRIMED-2): randomized controlled trial

FUNDING

Patient Centered Outcomes Research Institute (PCORI)

VERSION DATE

January 6, 2021

SPECIFIC AIMS

Concisely state the objectives of the study and the hypothesis being tested.

Due to COVID-19 there has been a sharp reduction in the number of colonoscopies since Feb 2020. This is predicted to lead to delayed diagnosis in more than 18,000 patients across the US.ⁱ Recovery efforts are underway to plan for resuming these non essential health care services. However, if patients are not willing or able to come back to get routine cancer screening, then these testing delays may have a significant impact on cancer mortality rates. There is very limited data examining patients' attitudes and concerns about seeking cancer screening in this environment. The aims of this study are to:

Aim 1: Assess anxiety, COVID risk tolerance, cancer worry, willingness to screen, barriers to colonoscopy, and preference for alternative colon cancer screening options for patients aged 45-75 who had their screening or surveillance colonoscopy delayed due to the pandemic.

Aim 2: Examine effectiveness of using a shared decision making approach with patients on the waitlist to decide about rescheduling their colonoscopy. We will randomly assign patients to receive SDM tools or usual care. We will test hypotheses that compared to the control group, patients in intervention arm will (a) report higher shared decision making; (b) have stronger intention to follow through with colon cancer screening (whether colonoscopy, stool-based test or other approach); and (c) have less decisional conflict.

Aim 3: Follow all patients on the waitlist and examine wait times and completed colonoscopies to determine whether these differ by patient characteristics, including gender, age, race and ethnicity, adjusting for cancer risk.

BACKGROUND AND SIGNIFICANCE

Provide a brief paragraph summarizing prior experience important for understanding the proposed study and procedures.

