For Aim 2, we will conduct a randomized controlled trial that will enroll patients who have to reschedule colonoscopies. We will randomly assign about 900 patients who are on the waitlist to either intervention or control arm. The intervention arm will receive a shared decision making worksheet that will cover (a) presenting pros and cons of three screening options (first available colonoscopy (wait time estimated to be ~6 months), stool-based test (with consideration that if positive, a follow-up colonoscopy may still be delayed ~3 months), and delay colonoscopy one year); (b) contact information for rescheduling their colonoscopy; and (c) contact information to connect with staff if they have questions or need more information. GI clinicians will be recruited and complete an online SDM training prior to their visit with patients who have more questions and request a GI visit. The control group will receive the standard department guidance and policies on scheduling. We will invite patients to complete a survey to track SDM, decisional conflict, overall anxiety and cancer worry, preference for colonoscopy, concerns about accessing health care-and we will also track any testing received within 6 months. We estimate sending a survey to about 700 patients across both arms and receiving 450 completed surveys.

For Aim 3, we will follow all MGH patients who had their screening or surveillance colonoscopy delayed for 12 months and will document receipt of colonoscopy or other colon cancer screening test, and if they got a colonoscopy, will calculate the wait time for colonoscopy for all of the patients on the waitlist. We will track demographic information, age, gender, race and ethnicity, primary language, zip code. We estimate that there are about 5,000 patients who have had their colonoscopy delayed that will be followed in this chart review portion of the study.

Table 1: Eligibility for patient participants

Eligible	Ineligible

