
• Adults, age 45-75• Had screening or surveillance colonoscopy delayed due to COVID-19• Either due for first screening colonoscopy or a routine screening or surveillance colonoscopy for low to moderate risk patients (as indicated by 3-10 year recommended follow up frequency on prior test)	
• Diagnostic colonoscopy• High risk for colorectal cancer as indicated by 1 year follow up schedule• Prior history of colon cancer• Unable to read or write in English or Spanish (Aim 1 and 2 only)• Have not already rescheduled or completed their colonoscopy

Briefly describe study procedures. Include any local site restrictions, for example, “Subjects enrolled at Partners will not participate in the pharmacokinetic portion of the study.” Describe study endpoints.

Working closely with co-investigators and staff in GI department, study staff will create a master waitlist of patients who had a previously scheduled colonoscopy postponed, who had a referral for a colonoscopy that has not been processed, and/or who should have been contacted by the GI department to schedule a colonoscopy but were not due to COVID-19 restrictions. Study staff will confirm that they meet the eligibility criteria as outlined in Table 1. Study staff will also use RDPR and Epic to confirm eligibility if needed.

For the patient surveyed in both the cross-sectional study and the randomized trial, study staff will send each subject a packet that includes a cover letter signed by the Director of Quality and Safety for the department inviting their participation and providing information to opt-out of the study, an information sheet describing the study, an incentive (\$10), and the survey. Patients will also be given option to complete the survey via RedCap. Patients will indicate consent by returning the survey. Survey responses will be entered into RedCap and analyzed by the study team. On the survey, patients will be able to indicate if they are interested in participating in an optional short interview to follow-up on their survey responses. Staff will contact a selected subset of patients who agreed to set up the short interview.

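### Should hypothesis 1 specify a risk difference with confidence interval and a covariate-adjusted estimate beside the Fisher exact test?

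*SAP*

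**What the plan says.** SAP, Statistical methods, hypothesis 1: uptake is analysed as "the percentage of patients who had either stool test or colonoscopy in each arm compared using a Fisher Exact test". A second sentence adds time to screening: "We also used cumulative incidence function to compare time to screening completion". Neither names an effect measure, an interval or covariates. Hypotheses 2 and 3 use an unadjusted t-test and chi-square tests. The only regressions in the SAP are the exploratory subgroup interaction models.

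SAP, Sample Size: 800 participants give 81% power for a 10-point difference in uptake. No control rate, alpha or sidedness is stated.

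SAP, Randomization and blinding: "All 800 patients were followed to track colon cancer screening tests completed".

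SAP, Outcomes: "Additional measures were collected to describe the sample and used as covariates". Seven measures follow: recent discussion with a provider, physical health, literacy, screening history, COVID-19 worry, worksheet use and coaching exposure. Separately, "Basic demographics for the full sample were collected via chart review".

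Protocol, Specific Aims, Aim 3: the study will "examine wait times and completed colonoscopies to determine whether these differ by patient characteristics, including gender, age, race and ethnicity, adjusting for cancer risk". For that aim the Research Design section adds: "We will track demographic information, age, gender, race and ethnicity, primary language, zip code". Table 1 limits surveillance and routine screening entries to those "for low to moderate risk patients (as indicated by 3-10 year recommended follow up frequency on prior test".

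**The concern.** Three things look wrong together. First, the trial is sized on a difference in rates, yet the plan does not say that this difference will be estimated with its uncertainty. A non-significant p-value could then be read as no effect when the data still allow the planned benefit.

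Second, age, sex, race and ethnicity are on file for everyone and Aim 3 studies these factors in relation to completed colonoscopy, yet no main analysis adjusts for them. If they predict uptake, precision is given away.

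Third, the SAP calls seven measures covariates, but the tests for hypotheses 1 to 3 take none. Worksheet use and coaching exposure arise after randomisation, so a reader would want to know whether they entered a treatment-effect model.

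**Working it through.** **Inputs.** From the SAP: 800 patients, 1:1 (taken as 400 per arm), a 10-point difference, 81% power. Assumed because not stated: two-sided alpha 0.05, the control rate, and the share of outcome variance explained by chart factors (R²).

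**1. The plan's own figure.** Power = Φ[(0.10 − 1.96·SE₀)/SE₁], with SE₀ pooled and SE₁ unpooled.
- 45% vs 55%: SE₀ = √(2 × 0.25/400) = 0.03536; SE₁ = √((0.2475 + 0.2475)/400) = 0.03518. Φ[(0.10 − 0.0693)/0.03518] = Φ(0.873) = 80.9%.
- 40% vs 50%, and by symmetry 50% vs 60%: 81.25%.
- 35% vs 45%: 82.4%.

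The 81% is therefore reproduced for control rates of about 40% to 50%. Exact power of the Fisher test itself is 79.3% to 79.4% for those control rates, within 2 points of the stated figure.

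**2. Is information lost without a specified interval?** The analysis itself consists of the two percentages. With 400 per arm, the 95% half-width is 1.96·√[(p₀(1−p₀) + p₁(1−p₁))/400].

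| Control vs intervention | Half-width (points) |
|---|---|
| 30% vs 40% | 6.6 |
| 40% vs 50% | 6.9 |
| 45% vs 55% | 6.9 |
| 50% vs 60% | 6.9 |

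Worked case: 200/400 vs 180/400 has Fisher p = 0.18. From the percentages alone, the difference is 50 − 45 = 5.0 points, SE = √((0.25 + 0.2475)/400) = 0.0353, and the interval is 5.0 ± 6.9, or −1.9 to 11.9. The Newcombe interval is −1.9 to 11.8. Anyone holding the reported percentages can see that both 0 and 10 points remain possible.

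The cumulative incidence curves are also on the absolute scale. With every patient followed and nobody censored before six months, their heights at six months are the same two percentages.

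An interval and the Fisher test can disagree at the border. For 208/400 vs 180/400, the Newcombe interval is 0.1 to 13.8 and Fisher p = 0.056. Fisher, as the named test, decides in such a case.

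**3. What would adjustment gain?** Multiply the SE by √(1 − R²). At 45% vs 55% (SE 0.03518), approximate Wald power is Φ[0.10/(SE·√(1−R²)) − 1.96].

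| Assumed R² | Half-width (points) | Wald power |
|---|---|---|
| 0 | 6.89 | 81.1% |
| 2% | 6.83 | 81.9% |
| 5% | 6.72 | 83.1% |
| 10% | 6.54 | 85.0% |

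The narrowing is 0 to 0.35 points, or 0% to about 5%. The power column does not apply to this trial: the Fisher test decides, and a supportive estimate would not change that decision.

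**4. Does Aim 3 show that these factors predict uptake?** Aim 3 asks whether wait times and completed colonoscopies differ by patient characteristics, in about 5,000 waitlisted patients followed for 12 months. Hypothesis 1 concerns a stool test or colonoscopy within 6 months in 800 randomised patients. An open question about a related outcome in a wider group gives no value for R². Table 1 also narrows the spread in cancer risk at entry.

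**5. The covariate sentence.** Four of the seven measures correspond to factors in the interaction models: physical health (overall health), screening history, COVID-19 worry and coaching exposure. Recent discussion, literacy and worksheet use match no named model. The SAP sentence gives two purposes, description and covariate use, so these three can be read as descriptive. Most of the seven look like survey items, available only for respondents (300 planned), so they could not adjust an analysis of all 800.

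**The case for a change.** The strongest contrary case is that the fix is nearly free. One interval and one sentence would align the reporting with a sample size built on a difference, and the patients and chart data are already in hand. Adjustment for baseline factors keeps the comparison valid and usually helps a little. The text also supports the observation: no interval is named, and three measures labelled covariates have no model.

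The factual part stands. What does not follow is that the plan is deficient. No bias is alleged, no stated figure is wrong, and the missing interval is something an analyst reports as a matter of course.

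The adjusted model is the weaker half. The SAP is dated August 25, 2021. The last wave was mailed on October 22, 2020, so its six-month window closed about April 22, 2021, some four months earlier, and the analysing statistician was not blinded. A covariate set chosen now would need a post hoc label and would add analyst discretion, in return for at most about 0.4 points of half-width.

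**Conclusion.** No change to the plan. Carried out as written, hypothesis 1 gives a valid test and two percentages from which the risk difference and its interval follow directly (half-width 6.6 to 6.9 points for control rates of 30% to 50%). The missing interval is a reporting detail that analysts fill sensibly. The covariate sentence is loose drafting that a line in the report can settle, by saying which measures entered the interaction models and which were descriptive. Covariate adjustment is optional. Its benefit is 0% to 5% in interval width under an assumed R² of 0 to 10%, which the documents do not establish, and the associated power gain cannot be realised while Fisher decides.

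This rests on 400 per arm, two-sided alpha of 0.05, complete six-month chart follow-up as the SAP states, and publication of the two uptake percentages.
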